The 8, 16, and 24 mg human doses provide lung exposures (0.004, 0.008, and 0.012 mg of [REDACTED] mRNA deposited per g lung, respectively) that are comparable to those of the lower doses given to the rats and non-human primates in the single and multiple-dose toxicity studies (0.19 to 0.77 mg/kg dose levels corresponding to 0.0065 to 0.0154 mg of [REDACTED] mRNA deposited per g lung, and calculated HEDs of 13 to 31 mg). These dose levels deposited significant levels of [REDACTED] mRNA in the lungs of both species compared to endogenous levels and, importantly, expressed detectable levels of human CFTR protein by immunohistochemistry at 24 hours post-treatment. Persistence of the human CFTR protein was also detected in rats at 7 days post-treatment following a single dose of MRT5004 at 0.53 mg/kg (HED of 22 mg); and at 28 days post-treatment following 5 once weekly doses of MRT5005 at 0.77 mg/kg (HED of 31 mg). These observations supported the dose levels and weekly dosing interval of MRT5005 that will be investigated in Parts A and B of this study.

The 4 mg dose strength was selected for evaluation in Part D based on observations of mild to moderate febrile reactions reported in 7 subjects who received a single dose of MRT5005 ranging from 8 to 24 mg (1 subject each in the 8 mg, 16 mg, 20 mg single dose groups in Part A, 3 subjects in the 24 mg single dose group in Part A, 1 subject in the 16 mg multiple dose group in Part B who discontinued treatment after first dose). Evaluation of a lower dose will help determine whether febrile reactions associated with MRT5005 are dose dependent or idiosyncratic. Investigation of a daily dosing regimen in Part D is attractive given the estimated short half-life of CFTR mRNA (14 hours) and translated CFTR protein (29 hours). The anticipated safety of 4 mg administered daily for 5 days (20 mg total) can be predicted from the safety and tolerability of 20 mg administered as a single dose in Part A.

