4.5.1. Reasons for Discontinuation and Individual Stopping Rules

Individual Subjects will be discontinued by the Investigator if they meet any of the stopping rules described below:

1. A significant febrile reaction defined as \geq Grade 2 fever (>39.0 °C) associated with systemic symptomatology (eg, body aches, malaise, nausea) within 24 hours following administration of IP.
2. An absolute decrease in predicted FEV1 of at least 25% compared to the baseline value (defined as the average of the Day -1 and Day 1 pre-dose values) during the 5-week treatment period in Part B or through Day 11 (1 week post-5th dose) in Part D that cannot be explained, in the opinion of the PI, by the underlying disease of CF and that is confirmed on 2 separate occasions at least 3 days apart
3. A suspected moderate to severe allergic/hypersensitivity reaction, including but not limited to anaphylaxis, generalized rash, edema or bronchospasm possibly related to drug treatment
4. Deterioration of liver function as explained below and in Section 8.1.4.1
 - a. Elevation of ALT or AST to >5 x ULN in a subject regardless of baseline value
 - b. Elevation of ALT or AST to >3 x ULN in a subject with a normal baseline or elevation of >3 x ULN from the subject's actual baseline if not normal, with the

appearance of fatigue, nausea, vomiting, right upper quadrant pain or tenderness, fever, rash, and/or eosinophilia (>5%).

c. Elevation of ALT or AST to >3x ULN in a subject with a normal baseline or elevation of >3x ULN from the subject's actual baseline if not normal, and total bilirubin >2x ULN or INR >1.5.

If any of the above criteria is met by a Part B or Part D subject who has not completed dosing with IP, treatment must be interrupted immediately and the Medical Monitor notified of this action.

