## 2.4 Treatment Regimens and Randomization

In all three parts of the study, subjects will be randomized to receive either MRT5005 or placebo (normal saline) in a 3:1 ratio. Subjects will receive a single dose in Part A, 5 weekly doses in Part B, and 5 consecutive daily doses in Part D. The 8 mg dose level of MRT5005 will be the SAD starting dose in Part A followed by sequential escalation to the 16 mg and 24 mg dose levels of MRT5005. An additional 20 mg treatment group was added to Part A after blinded safety information from the 24 mg group revealed the occurrence of febrile reactions in 3 of 4 subjects. The 8 mg dose level of MRT5005 will be the MAD starting dose in Part B, followed by sequential escalation to the 16 mg and 20 mg dose levels of MRT5005. An additional 12 mg group was added to Part B to explore the safety profile at an intermediate dose level that was not investigated as a single dose in Part A. The 12 mg dose level may begin enrollment in parallel with the 16 mg dose level. The enrollment and treatment of the 4 subjects within each MAD dose group will be staggered by at least 2 weeks (the next subject in the dose group will only be enrolled and treated when the previous subject has received their second dose and there is approximately 1 week of safety follow-up), with the exception of the 12 mg dose group in Part B which may not require staggered treatment. In Part D, 8 subjects will be randomized in a 3:1 ratio to receive 5 doses of either 4 mg MRT5005 or placebo, administered at 1 dose per day for 5 consecutive days. Because single doses up to 20 mg, as well as 5 weekly doses up to 16 mg have been tolerated in Parts A and B, the enrollment and treatment of the 8 subjects within Part D will not be staggered. During the treatment of subjects in Part D, should AEs occur that indicate the study drug is not tolerated well, the enrollment and treatment of subjects may be terminated by the PSRC and Sponsor, and enrollment and treatment of a lower dose strength may be considered in the remaining subjects in the cohort. For example, if the tolerability of the 4 mg daily dose level is found to be unacceptable, then the 2 mg dose level can be considered for investigation. Subjects will not be allowed to participate in more than 1 part of the study.

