Treatment-emergent febrile reactions and hypersensitivity reactions will be presented as a count of febrile reactions, febrile reactions by severity, hypersensitivity reactions, and hypersensitivity reactions by severity. Additionally, the table will reflect the count and percentage of subjects experiencing the following: any febrile reaction, any febrile reaction by severity, any hypersensitivity reaction, and any hypersensitivity reaction by severity. The summary will be for all subjects in the safety analysis set by dose group for each study part. In addition, the summary of treatment-emergent febrile reactions and hypersensitivity reactions will be presented for all subjects in the safety analysis set for the study overall by pooled treatment group. Febrile reactions will be identified based on a preferred term of body temperature increased or preferred term of pyrexia within the 24 hours after completion of

nebulization on any dosing day with at least one other systemic symptom reported as a preferred term of headache, arthralgia, myalgia, fatigue, chills, nausea, or vomiting within the 24 hours after completion of nebulization on any dosing day. Severity grade for febrile reactions will be based on the maximum severity of the preferred terms comprising the febrile reaction. Hypersensitivity reactions will be identified based on a preferred term of hypersensitivity within the 24 hours after completion of nebulization on any dosing day.

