**Notes:**

- 1) The first page will be "Part: All Study Parts" with "Time Interval: Overall" and will include all AEs across all study parts. The subsequent page will be: "Part: All Study Parts" with "Time Interval: 1 month post-dose"
- 2) In the column headers, report the number of subjects who were at risk for an AE at the start of the interval.
- 3) Sort by descending order of overall (Pooled MRT5005 + Pooled Placebo) frequency.
- 4) Summarize number of events, so subjects with multiple TEAEs in preferred term in a time interval are counted more than once.

Table 14.3.2.4 (AE\_TAM\_F\_X)

Summary of Treatment-Emergent Febrile Reactions in First 24 Hours After Completion of Nebulization by Preferred Term and Dose Group  
Population: Safety Analysis Set

	MRT5005 Xmg N=xx n (%)	MRT5005 Xmg N=xx n (%)	MRT5005 Xmg N=xx n (%)	Pooled Placebo N=xx n (%)
Number of Febrile Reactions Reported	xx	xx	xx	xx
Number of Subjects with Any Febrile Reactions Reported [1]	xx (xx.x)	xx (xx.x)	xx (xx.x)	xx (xx.x)
Number of Febrile Reactions by Severity [2]				
Mild	xx	xx	xx	xx
Moderate	xx	xx	xx	xx
Severe	xx	xx	xx	xx
Number of Subjects with Febrile Reactions by Maximum Severity [3]				
Mild	xx (xx.x)	xx (xx.x)	xx (xx.x)	xx (xx.x)
Moderate	xx (xx.x)	xx (xx.x)	xx (xx.x)	xx (xx.x)
Severe	xx (xx.x)	xx (xx.x)	xx (xx.x)	xx (xx.x)

[1] AE\_F05

[2] AE\_F17c

[3] AE\_F07a

Note: AE\_F17a

Listing Source: AE\_LAK\_F\_X

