DM	CFTR	DM_F02	[2]	CFTR Modulator use at baseline was defined as a concomitant CFTR modulator that was in use at the start of treatment, or a CFTR modulator with missing start date.
CM	Percent	CM_F01	Note:	n = Number of subjects that reported at least 1 medication within an Anatomic Class, Therapeutic Class, and Medication Term; (%) = Percentage of subjects among the population analyzed (N).
CM	Count	CM_F02	Note:	A subject that reported more than 1 medication for a particular Anatomic Class was counted only once for each Anatomic Class.
CM	Count	CM_F03	Note:	A subject that reported more than 1 medication for a particular Therapeutic Class was counted only once for each Therapeutic Class.
CM	Count	CM_F04	Note:	A subject that reported more than 1 medication for a particular Medication Term was counted only once for each Medication Term.
CM	Order	CM_F05	Note:	Medications were presented in order of decreasing frequency, by Anatomic Class, Therapeutic Class, and Medication Term.
CM	Definition	CM_F06	Note:	Concomitant medications included all medications in use at date of first study drug dose or started after date of first study drug dose, any medications that started prior to the day of first dose of study drug with missing stop date, any medications with missing start and stop dates or were classified as ongoing.
CM	Definition	CM_F07	Note:	Prior medications included all medications that stopped prior to the day of first dose of the study drug, medications that started prior to the day of first dose of study drug with missing stop date or medications with missing start and stop dates.
CM	Dictionary	CM_F08	Note:	Anatomic Class, Therapeutic Class, and Medication Term were based on the WHO Drug Global (2020-SEP) coding dictionary.
MH	Count	MH_F01	Note:	If a subject had more than 1 medical history event within a system organ class, the subject was counted only once in that system organ class. If a subject had more than 1 medical history event that coded to the same preferred term, the subject was counted only once for that preferred term.
AE	Count	AE_F05	[1]	Subjects that experienced 1 or more adverse events were counted once.
AE	Count	AE_F06a	[2]	If a subject experienced more than 1 adverse event, the subject was counted only once for the closest relationship to IP. AEs with missing relationships to IP were classified as being Related to IP.

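### The percentage of subjects with a febrile reaction is not comparable between Part A (one post-dose window) and Part D (five), and the febrile tables give no figure that is

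*SAP*

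**What the plan says.** SAP section 9.4 builds the febrile reaction from adverse event terms tied to dosing: a temperature term, for example "preferred term of pyrexia within the 24 hours after completion of" nebulization, plus at least one other listed systemic symptom in the same kind of window. Reactions "will be presented as a count of febrile reactions", and at subject level "the table will reflect the count and percentage of subjects experiencing the following: any febrile reaction". The shells of Tables 14.3.2.4 (by dose group, one table per part) and 14.3.2.5 (all parts, pooled MRT5005 against pooled placebo) carry this through. The event count has no denominator, and the row "Number of Subjects with Any Febrile Reactions Reported" is n (%) on subjects. Its footnote states "Subjects that experienced 1 or more adverse events were counted once".

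SAP section 2.4 sets the number of windows: "Subjects will receive a single dose in Part A, 5 weekly doses in Part B, and 5 consecutive daily doses in Part D". Doses actually given are summarised separately, in Table 14.1.4.

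Protocol section 2.2.3 gives the reason for Part D: "Evaluation of a lower dose will help determine whether febrile reactions associated with MRT5005 are dose dependent or idiosyncratic". It lists seven subjects with febrile reactions: 1, 1, 1 and 3 in the Part A 8, 16, 20 and 24 mg groups, and one in the Part B 16 mg group who stopped after the first dose.

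**The concern.** A subject dosed five times has five chances to be counted as a reactor; a subject dosed once has one. The subject percentage therefore mixes risk per dose with number of doses. Where the number of doses is the same, this does no harm. It does harm when Part D (4 mg, five doses) is read against the Part A single-dose groups, and section 2.2.3 invites that reading, since six of its seven reactors were in Part A.

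The direction is awkward. Extra windows can only raise the low-dose percentage relative to the single higher doses, so a real fall in per-dose risk at 4 mg could be masked. The size of the distortion depends on how far reactions are a fixed trait of the subject, which is close to what Part D was added to find out.

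**Working it through.** **Inputs.** Planned subjects are 16, 16 and 8 in Parts A, B and D (protocol synopsis), a total of 40 as stated. At 3:1 allocation that is 12, 12 and 6 active, and 4, 4 and 2 placebo. Doses per subject are 1, 5 and 5 (SAP 2.4). The seven reactors in protocol 2.2.3 add up: 1 + 1 + 1 + 3 + 1 = 7. The documents give no expected febrile rate, so every per-dose risk below is an assumption, shown over a range.

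**Planned windows.**
- Active: 12×1 + 12×5 + 6×5 = 102 over 30 subjects, or 3.4 each.
- Placebo: 4×1 + 4×5 + 2×5 = 34 over 10 subjects, or 3.4 each.

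The pooled contrast is therefore balanced on planned windows, and within any one part every group has the same planned number.

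**Part A against Part D, independent doses.** With per-dose risk q, the chance of at least one reaction is q over one window and 1 − (1 − q)^5 over five.

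| q | one window | five windows | ratio |
|---|---|---|---|
| 5% | 5% | 22.6% | 4.5 |
| 10% | 10% | 41.0% | 4.1 |
| 20% | 20% | 67.2% | 3.4 |

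In reverse, a table entry of 33.3% implies a per-dose risk of 33.3% in Part A, but 1 − (1 − 0.333)^(1/5) = 7.8% in a five-dose group.

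**Allowing correlation within a subject.** Under an assumed beta-binomial model with q = 10%, the five-window percentage is 35%, 27% and 21% for within-subject correlations of 0.1, 0.3 and 0.5. At a correlation of 1 it is 10%, the same as in Part A.

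**What the table would hide.** One reactor among 3 subjects in a Part A group is 33.3% of subjects and 33.3% of doses. Two of 6 Part D subjects reacting once each is also 33.3% of subjects, but 2/30 = 6.7% of planned doses.

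**Can the order of doses reverse?** Compare 6 subjects at 4 mg (five windows) with 3 at a single 20 mg dose, assuming independence. At 10% against 20% per dose, the 4 mg group shows the higher percentage with probability 0.68 and the lower with 0.17. With 33% at 20 mg, the higher/lower probabilities are 51%/31% for q = 10% at 4 mg, 29%/52% for q = 5% and 14%/66% for q = 2%. Reversal is possible but depends on the scenario.

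**The case against.** The case against is substantial, and most of it limits the point.

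- **No planned table sets one window beside five by dose group.** This stands. The mismatch arises only when a reader carries a percentage from the Part A table to the Part D table. A reader might infer that the pooled active-placebo comparison is biased; at 3.4 planned windows per subject in each arm, it is not. Only the pooled percentage itself is a mixture.
- **A like-for-like comparison exists already.** Part B gives five doses at 8, 12, 16 and 20 mg against five at 4 mg in Part D. This stands on planned windows, but it leaves out the Part A reactors on whom the rationale mainly rests.
- **Doses given are reported.** A reader might infer that the plan never shows them. Table 14.1.4 shows how many subjects had 1 to 5 doses, so totals follow by addition. They are simply not linked to the febrile tables.
- **Stopping after a reaction.** Protocol 4.5.1 ends dosing after "A significant febrile reaction defined as" set out there. A reader might infer that this distorts the any-reaction percentage. It cannot, because a stopped reactor is already counted. The per-dose rate is the measure affected. If one of three subjects reacts at dose 1 and stops, while the other two complete without reacting, the rate is 1/11 = 9.1% of doses given against 1/15 = 6.7% of doses planned.
- **A first-dose view partly exists.** Table 14.3.1.2 has a Study Day 1 page in every part. It works by single preferred term and calendar day, so it neither forms the composite reaction nor applies the 24-hour window.
- **Subject incidence is a fair measure of a regimen.** This stands. Protocol 2.2.3 itself relates five doses of 4 mg to a single 20 mg dose, so the subject percentage should stay.

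**Conclusion.** The point holds in a limited form. The febrile tables contain no statistic that can be read like-for-like between Part A and Part D, although the stated purpose of Part D calls for that reading. The gap is at most about 3.4-fold to 4.1-fold for per-dose risks of 20% to 10%. That ceiling assumes the same risk at every dose and independence between doses. It falls to about two-fold at a within-subject correlation of 0.5 (10% reading as 21%) and to nothing if susceptibility is wholly subject-specific.

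The stronger reading, that the planned percentages would probably put 4 mg above single 20 mg, is not supported. It rests on one choice of risks at the independence extreme, and other plausible choices give the opposite order. All analyses are descriptive, so no error rate or sample size is affected. This is an inexpensive improvement in interpretability, not a flaw in the trial's conduct.

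**What to change.** Keep the percentage of subjects with any febrile reaction. Add to Tables 14.3.2.4 and 14.3.2.5, with a matching sentence in SAP section 9.4:

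1. The number and percentage of subjects with a febrile reaction within 24 hours after their first dose. This gives every dosed subject exactly one window in every part, needs no independence assumption, and should be named as the figure for comparisons across parts.
2. Doses administered in each column, and febrile reactions per dose administered, labelled descriptive.

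Dosing times and adverse event onset relative to the end of nebulization are already planned for the listings, so no new data are needed. The cost is a few rows. The downside is that the per-dose figure is correlated within subject and is affected when reactors stop dosing early; a footnote should say so.

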4.5.4. Dose Group Stopping Criteria

IP administration will be halted for all subjects in a dose group, as well as any subjects in an ongoing higher dose group if any of the following stopping criteria are met:

- a. Two subjects in a dose group experience a significant febrile reaction (defined as \geq Grade 2 fever [>39.0 °C] associated with systemic symptomatology [eg, body aches, malaise, nausea]) within 24 hours following administration of IP.
- b. Two subjects in a dose group experience a suspected moderate to severe allergic/hypersensitivity reaction, including but not limited to anaphylaxis, generalized rash, edema or bronchospasm possibly related to drug treatment.

To determine whether this dose group stopping rule has been met, the relevant data will be reviewed by the PSRC. The treatment assignment of one or more subjects may be unblinded at the request of the PSRC, as described in Section 3.4.1.2. Following this review, the PSRC will decide if the dose group and other ongoing higher dose groups will:

- Resume unchanged or
- Resume with modifications to the protocol or
- Be terminated.

The Sponsor is responsible for notifying the relevant regulatory authorities and the Investigator is responsible for promptly notifying the relevant IRB of the decision.

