4.5.5. Part D Stopping Criterion

IP administration will be halted for all subjects in Part D if the following stopping criterion is met:

- a. Three subjects experience Grade 1 fevers (38.0 to 39.0 °C) associated with systemic symptomatology (eg, body aches, malaise, nausea) onset within 24 hours following administration of IP on ≥ 3 separate occasions.

To determine whether this dose group stopping rule has been met, the relevant data will be reviewed by the PSRC. The treatment assignment of one or more subjects may be unblinded at the request of the PSRC, as described in Section 3.4.1.2. Following this review, the PSRC will decide if the dose group and other ongoing higher dose groups will:

- Resume unchanged or
- Resume with modifications to the protocol or
- Be terminated.

The Sponsor is responsible for notifying the relevant regulatory authorities and the Investigator is responsible for promptly notifying the relevant IRB of the decision.

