AE	Definition	AE_F17a	Note:	Febrile reactions were identified based on a preferred term of body temperature increased or preferred term of pyrexia within the 24 hours after completion of nebulization on any dosing day with at least one other systemic symptom reported as a preferred term of headache, arthralgia, myalgia, fatigue, chills, nausea, or vomiting within the 24 hours after completion of nebulization on any dosing day.
AE	Definition	AE_F17b	Note:	Hypersensitivity reactions were identified based on a preferred term of hypersensitivity within the 24 hours after completion of nebulization on any dosing day.
AE	Definition	AE_F17c	[2]	Severity grade for each febrile reaction was based on the maximum severity of the preferred terms comprising the febrile reaction. Febrile reactions with missing severity were counted as Severe.

Data Type	Footnote Type	Code	Prefix	Footnote
AE	Interval	AE_F18	Note:	The 1 month post-dose time interval is defined as through Day 29 for Part A, through Day 57 for Part B, through Day 32 for Part D.
AE	Count	AE_F19	Note:	N represents the number of subjects in a given dose group that experienced an adverse event.
EG	Baseline	EG_F01	Note:	The baseline value was defined as the Day -1 ECG measurement.
EG	Baseline	EG_F01D	Note:	The baseline value was defined as the screening ECG measurement.
EG	Schedule	EG_F02	Note:	Only ECGs scheduled per the protocol were summarized.
EX	Count	EX_F01	Note:	Full dose refers to completion of all nebulizers as planned; partial dose refers to incomplete nebulization. Full and partial dose are independent of the presence or absence of excess residual in the medication chamber.
VS	Schedule	VS_F01	Note:	The final recording during nebulization for blood pressure, pulse rate, and pulse oximetry was counted as the 'DAY 1 (0 HR POST-DOSE)' value.
RE	Baseline	RE_F01	[1], [3]	The baseline value was defined as the average of the results from testing on Day -1 and at pre-dose on Day 1.
RE	Baseline	RE_F01D	[1], [3]	The baseline value was defined as the result from testing pre-dose on Day 1.
RE	Baseline	RE_F01O	[1], [3]	The baseline value was defined as the average of the results from testing on Day -1 and at pre-dose on Day 1 for Part A and Part B, and defined as the result from testing pre-dose on Day 1 for Part D.
CFQ	Baseline	CFQ_F01	Note:	The baseline value was defined as the Day -1 CFQ-R respiratory domain score.

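### The SAP's febrile-reaction symptom list omits malaise, and no row of the febrile-reaction tables isolates reactions that meet the protocol's temperature-based definition

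*SAP*

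**What the plan says.** Protocol 4.5.1 discontinues a subject for a significant febrile reaction: a fever of Grade 2 or higher (above 39.0 °C) that is "associated with systemic symptomatology (eg, body aches, malaise, nausea) within 24 hours following administration of IP". Protocol 4.5.4(a) halts a dose group when two subjects have such a reaction, with the same symptom wording: "associated with systemic symptomatology [eg, body aches, malaise, nausea]) within 24 hours following administration of IP". Protocol 3.4.1.2 uses this definition for notifying the Protocol Safety Review Committee (PSRC), and SAP 2.6 and 2.7 restate it. The Part D criterion in Protocol 4.5.5 works one grade lower: "Three subjects experience Grade 1 fevers (38.0 to 39.0 °C) associated with systemic symptomatology (eg, body aches, malaise, nausea) onset within 24 hours". In all of these places the symptom list is open, and malaise is one of its three examples.

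For the analysis, SAP 9.4 and footnote AE_F17a require a preferred term of pyrexia or body temperature increased, together with "at least one other systemic symptom reported as a preferred term of headache, arthralgia, myalgia, fatigue, chills, nausea, or vomiting". That list is closed. On grading, SAP 9.4 says: "Severity grade for febrile reactions will be based on the maximum severity of the preferred terms comprising the febrile reaction". Footnotes AE_F17c and AE_F07a repeat the rule and count missing severity as Severe.

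Tables 14.3.2.4 (by part and dose group) and 14.3.2.5 (pooled) show the number of reactions, the number of subjects, and Mild, Moderate and Severe rows. Neither has a row by temperature or by fever grade.

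**The concern.** Fever is the tolerability signal that shaped this trial. The 20 mg single-dose group was added after febrile reactions in 3 of 4 subjects at 24 mg, and Part D was added to learn whether the reactions are dose dependent or idiosyncratic (Protocol 2.2.3 and 3.1). Tables 14.3.2.4 and 14.3.2.5 are the dedicated summaries for that question.

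A reader will expect to find in them every reaction that the protocol treats as significant, and to be able to tell those reactions from milder ones. The SAP's definition does not secure either. An event can meet the protocol's definition and go uncounted because its accompanying symptom was coded to malaise. The severity rows do not separate fevers above 39.0 °C from lower ones. Nothing in the SAP explains why a named example was left out when the list was closed.

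**Working it through.** There is no sample size, power or error-rate figure to reproduce; Protocol 9.6 and SAP 2.5 say that the sample size has no statistical basis. The check compares the definitions and then works through a small grid of cases.

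**Definitions side by side**

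| Source | Fever component | Symptom component | Malaise |
|---|---|---|---|
| Protocol 3.4.1.2, 4.5.1, 4.5.4; SAP 2.6, 2.7 | Grade 2 or higher, above 39.0 °C | open list, three examples | named |
| Protocol 4.5.5; SAP 2.7 | Grade 1, 38.0 to 39.0 °C | open list, same three examples | named |
| SAP 9.4; AE_F17a | pyrexia or body temperature increased, any grade | closed list, seven preferred terms | absent |

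Of the three protocol examples, only nausea appears by name in the SAP list. How a report of body aches would be coded is not in the documents, and nothing below depends on it.

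**Grid of cases.** Take fever grade 1, 2 or 3, one accompanying symptom (malaise or nausea), and symptom grade 1, 2 or 3: 3 × 2 × 3 = 18 combinations. Assume that fever terms are graded by temperature, as the protocol's rules do.

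- *Meeting the significant-reaction definition* (fever grade 2 or 3): 2 × 2 × 3 = 12.
- *Of these, not counted by the SAP* (malaise only): 2 × 3 = 6.
- *Counted by the SAP* (nausea): 3 × 3 = 9, each graded as max(fever grade, symptom grade).
- *SAP grade differs from fever grade*: 3 of 9. Fever 1 with nausea 2 gives Moderate; fever 1 with nausea 3 gives Severe; fever 2 with nausea 3 gives Severe.
- *SAP grade below fever grade*: 0 of 9. The shift is upward only.

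By table row, the nine counted cases fall as follows:

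| Row | Cases | Fever above 39.0 °C |
|---|---|---|
| Mild | 1 | 0 |
| Moderate | 3 | 2 |
| Severe | 5 | 4 |

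Moderate and Severe combined hold 3 + 5 = 8 cases. Of these, 2 + 4 = 6 meet the protocol definition and 2 are Grade 1 fevers, while the 6 malaise cases appear nowhere. So neither a single row nor their sum gives the protocol's set. These are counts of logical combinations, not estimates of frequency.

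**Effect of one subject.** SAP 2.5 gives 3 active subjects per dose group in Parts A and B, and 6 in Part D. One uncounted subject changes the displayed rate by 1/3 = 33.3 percentage points or 1/6 = 16.7 percentage points.

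**After the fix.** With malaise on the list, the 6 uncounted cases become 0, and a row defined on fever grade holds exactly the 12 that meet the definition. The severity rows still grade by worst component (now 6 of 18 cases above the fever grade), but they no longer have to do the work of the new row.

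**The case against.** The strongest reply has four parts.

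- *The protocol defines only the significant reaction, for stopping and PSRC notification.* It uses the plain term febrile reaction without defining it, so SAP 9.4 is free to give a broader descriptive definition, and an open list has to be closed before it can be programmed. This stands. It means that the tables need not equal the stopping rule. It does not explain leaving out a symptom that the SAP itself names in 2.6 and 2.7.
- *The event stays visible.* Listing 16.2.7.7 shows every adverse event in the window for any subject with a fever term, and Listing 16.2.7.8 shows all events in the window. Table 14.3.1.2 counts the two preferred terms separately. This stands and limits the harm. Listing 16.2.7.9, the dedicated one, uses the SAP definition and would omit the case, and a listing does not correct a tabulated rate.
- *Worst-component grading is a choice.* It is openly stated and, on the assumption above, shifts grades upward only, so a counted fever above 39.0 °C is never shown as Mild. This stands. A reader might infer that the rule is an error that should be replaced; the documents do not support that, because the protocol's grades describe the fever and the SAP's describe the composite reaction.
- *The missed case is narrow.* It needs malaise and none of the seven listed terms. This stands; no frequency is given.

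A reader might also argue from Protocol 8.1.7 that fatigue cannot stand in for malaise. That section puts the two in one item as alternatives, so it does not show this. The point rests only on the SAP matching by preferred term.

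**Conclusion.** The point holds as a reporting gap. A fever above 39.0 °C with malaise and none of the seven listed terms meets the protocol's definition of a significant febrile reaction, but would be missing from Tables 14.3.2.4 and 14.3.2.5 and Listing 16.2.7.9. Separately, no row of those tables identifies the reactions that meet the temperature-based definition, because a Grade 1 fever can be shown as Moderate or Severe.

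A reader might infer that dosing could wrongly continue. The documents do not support that: under Protocol 4.5.4 and 4.5.5 and SAP 2.7 the PSRC reviews the relevant data, not these tables.

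The size is 33 or 17 percentage points for each subject affected; how many would be affected cannot be derived from the documents. The conclusion assumes that such an event is coded to malaise as its own preferred term. The upward-only statement assumes that fever terms are graded by temperature.

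**What to change.** Two changes, both to reporting only:

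1. In SAP 9.4 and footnote AE_F17a, add malaise to the list of accompanying preferred terms. Listing 16.2.7.9 then picks it up as well.
2. In Tables 14.3.2.4 and 14.3.2.5, add one row for significant febrile reaction as defined in Protocol 4.5.1 (fever of Grade 2 or higher, above 39.0 °C, with systemic symptoms). The footnote should say which fever grade and which symptom terms the row uses.

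The worst-component severity rows can stay as they are. The cost is SAP wording, one footnote and one table row; no new data are needed, and no stopping rule or clinical decision changes. The one downside is that the reported febrile-reaction count may rise slightly.
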